3.2.4 Time to first subsequent therapy or death (TFST)

Time to start of first subsequent therapy or death (TFST) will be assessed. TFST is defined as the time from randomisation to the earlier of first subsequent therapy start date following study treatment discontinuation, or death. Subsequent therapies will be reviewed to assess which represent clinically important treatments intended to control ovarian cancer. Any patient not known to have died at the time of the analysis and not known to have had a further intervention of this type will be censored at the last known time to have not received subsequent therapy, i.e. the last follow-up visit where this was confirmed.

3.2.5 Time to second subsequent therapy or death (TSST)

Time to start of second subsequent therapy or death (TSST) will be assessed. TSST is defined as the time from randomisation to the earlier of the second subsequent therapy start date following study treatment discontinuation, or death. Any patient not known to have died at the time of the analysis and not known to have had a further intervention of this type will be censored at the last known time to have not received second subsequent therapy, i.e. the last follow-up visit where this was confirmed.

3.2.6 Time to study treatment discontinuation or death (TDT)

Time to permanent study treatment discontinuation or death (TDT) will be assessed. TDT is defined as the time from randomisation to the earlier of the date of permanent study treatment discontinuation or death. Any patient not known to have died at the time of analysis and not known to have discontinued study treatment will be censored based on the last recorded date on which the patient was known to be alive.

Note: Survival calls will be made in the week following the date of DCO for the analysis, and if patients are confirmed to be alive or if the death date is post the DCO date these patients will be censored at the date of DCO.

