11.1.2.6 Time to study treatment discontinuation or death (TDT)

Time to study treatment discontinuation or death (TDT) will be assessed (see Section 12.2.3.3). TDT is defined as the time from the date of randomisation to the earlier of the date of study treatment discontinuation or death. Any patient not known to have died at the time of analysis and not known to have discontinued study treatment will be censored based on the last recorded date on which the patient was known to be alive.

Note: Survival calls will be made in the week following the date of Data Cut Off (DCO) for the analysis, and if patients are confirmed to be alive or if the death date is post the DCO date these patients will be censored at the date of DCO.

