2 ANALYSIS SETS

2.1 Definition of Analysis Sets

Two main analysis sets are defined for this study for the analysis of patients who have been included in the study as part of the global enrolment.

Date 15 February 2022

Full analysis sets

Intention to treat (ITT): The primary statistical analysis of the efficacy of olaparib will include all patients who are randomised as part of the global enrolment. The primary analysis will compare the treatment groups on the basis of randomised treatment, regardless of the treatment actually received. Patients who were randomised as part of the global enrolment but did not subsequently go on to receive study treatment are included in the Full Analysis Set (FAS). Therefore, all efficacy and HRQoL data will be summarised and analysed using the FAS on an intention to treat (ITT) basis.

No centres will be provided with all of the treatment codes within that centre until completion of the study following the final analysis of overall survival.

Safety analysis set

All patients who received at least one dose of randomised investigational product, olaparib or placebo and are part of the global enrolment will be included in the safety analysis set (regardless of whether that was the randomised therapy intended or indeed whether, in rare cases, they received therapy without being randomised). Throughout the safety results sections, erroneously treated olaparib patients (those randomised to olaparib but actually received placebo) will be accounted for in the placebo treatment group. Erroneously treated placebo patients (those randomised to placebo but actually received olaparib) will be accounted for in the olaparib treatment group. Patients receiving treatment from more than one treatment arm will be accounted for based upon their initial treatment started

Table 1 Summary of Outcome Variables and Analysis Populations

Outcome Variable	Populations
Efficacy Data	
- PFS	FAS (ITT)
- OS, PFS2, TFST, TSST, TDT, symptom/HRQoL endpoints	FAS (ITT)
Study Population/ Demography Data	
- Demography characteristics (e.g. age, sex etc)	FAS (ITT)
- Baseline and disease characteristics	FAS (ITT)
- Important deviations	FAS (ITT)
- Medical/Surgical history	FAS (ITT)
- Previous anti-cancer therapy	FAS (ITT)
- Concomitant medications/procedures	FAS (ITT)
- Subsequent anti-cancer therapy	FAS (ITT)
Safety Data	
- Exposure	Safety
- Adverse Events	Safety
- Laboratory measurements	Safety
- ECGs	Safety
- Vital Signs	Safety

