2.2 Violations and Deviations

The important protocol deviations will be listed and summarised by randomised treatment group. None of the deviations will lead to any patients being excluded from any of the analysis sets described in Section 2.1. If the deviations are serious enough to have the potential to impact the primary analysis, sensitivity analyses may be performed.

The following general categories will be considered important deviations and be listed and discussed in the CSR as appropriate.

- Patients randomised but who did not receive olaparib/matching placebo.
- Patients who deviate from key entry criteria, which will be documented ahead of database lock.
- Baseline RECIST scan > 28 days before study treatment is started

Date 15 February 2022

- Baseline RECIST scan after randomised treatment is started.
- Patients who have a RECIST scan outside of a scheduled visit window on > 2
 occasions.
- Disallowed concomitant medication use.

Misrandomisations in terms of errors in treatment dispensing patients receiving treatment other than that to which they were randomised as well as incorrect stratifications, will also be summarised and listed. A misrandomisation is when a patient is not randomised or treated according to the randomisation schedule. It is envisaged that there will be 2 sub categories of this:

- (a) Patients who receive no treatment whatsoever for a period of time due to errors in dispensing of medication. Note, this is not due to tolerability issues where patients may stop taking drug.
- (b) The patient receives a treatment pack with a different code to their randomisation code. However, the actual treatment may still match the randomised treatment. For example, a patient is given randomisation code 0001, which according to the randomisation schedule is olaparib. However, at the randomisation visit they are given treatment pack 0003, but this still contains olaparib.

Patients who receive the wrong treatment at any time will be included in the safety analysis set as described in Section 2.1. During the study, decisions on how to handle misrandomisations will be made on an individual basis with written instruction from the study team leader and the study statistician.

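### TDT is censored by survival status, not treatment status, so a living patient who never took study drug can stay in the risk set as if still on treatment

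*SAP*

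**What the plan says.** SAP 3.2.6 defines the endpoint: "TDT is defined as the time from randomisation to the earlier of the date of permanent study treatment discontinuation or death". A patient with no recorded death who is "not known to have discontinued study treatment will be censored based on the last recorded date on which the patient was known to be alive". A note adds that where the survival call finds the patient alive, or the death falls after the cut-off, "these patients will be censored at the date of DCO". Protocol 11.1.2.6 carries the same rule ("not known to have discontinued study treatment will be censored based on the last recorded date").

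SAP Table 1 assigns "OS, PFS2, TFST, TSST, TDT, symptom/HRQoL endpoints" to the FAS. SAP 2.1 states that randomised patients who "did not subsequently go on to receive study treatment are included in the Full Analysis Set (FAS"). SAP 2.2 expects such patients, listing "Patients randomised but who did not receive olaparib/matching placebo" as an important deviation, and removes nobody from an analysis set because of a deviation.

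SAP 4.2.6 calls TDT supportive, makes no multiplicity adjustment, and repeats the analysis at each planned OS analysis.

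**The concern.** Knowing that a patient is alive says nothing about whether she is taking tablets. A censoring date for TDT should be the last date on which the patient was known to be on study drug. The plan uses the last date known alive, and the survival sweep moves that date to the data cut-off.

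Two kinds of patient are exposed:

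- **Never-dosed patients.** They have nothing to discontinue. If no discontinuation date is recorded and they are alive, the rule treats them as still on treatment.
- **Patients whose treatment status is lost but who are later found alive.** SAP 4.2.14 has sites seek vital status for withdrawn and lost patients from notes, general practitioners and registries, so the known-alive date can run well past the last confirmed dose.

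Treatment is planned for up to two years, with stated exceptions, so many patients stop at about the same time. A patient wrongly held in the risk set through that cluster has more influence than one patient in 391 normally would. At stake is the estimate for a named secondary endpoint.

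**Working it through.** **Text check.** Neighbouring endpoints have safeguards that TDT lacks.

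| Endpoint | Censoring date when no event is recorded |
|---|---|
| OS (SAP 3.2.3) | Last known alive, or DCO if confirmed alive |
| TDT (SAP 3.2.6) | Last known alive, or DCO if confirmed alive |
| TFST (SAP 3.2.4) | Last follow-up visit that confirmed no subsequent therapy |
| RECIST/CA-125 (SAP 3.2.7) | Randomisation, if there are no post-randomisation data |

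TDT follows the OS row. Protocol 5.8.1 has the discontinuation date recorded on the eCRF once a patient stops, but says nothing about one who never started.

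**The plan's own figures.** None is given for TDT. The only event-driven sizing is for PFS, and it reproduces: (1.960 + 1.282)² / [(2/3)(1/3)(ln 0.62)²] = 10.51 / 0.0508 ≈ 207 events, against 206 stated. This point does not depend on it.

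**Size, by hand.** Assumptions not in the documents for TDT: exponential times with medians of 21 and 13 months (borrowed from the PFS design, 13/0.62 ≈ 21), 261 and 130 patients, and everyone off drug between 24 and 25 months.

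- Reaching 24 months: 261 × 2^(−24/21) ≈ 118 olaparib and 130 × 2^(−24/13) ≈ 36 placebo, 154 in all, of whom 118/154 = 0.766 are on olaparib.
- One extra placebo patient at risk lowers the expected olaparib events at each stop by about 0.766/(n+1), where n is the number of others at risk. Summing 1/(n+1) for n = 1 to 154 gives 4.62, so the total is 0.766 × 4.62 ≈ 3.54.
- The log-rank variance is about 391 × (2/3)(1/3) ≈ 86.9. The shift in log HR is about 3.54/86.9 = +0.041, so an HR of 0.71 becomes about 0.74.
- One extra olaparib patient gives −0.234 × 4.62/86.9 ≈ −0.012, so 0.71 becomes about 0.70.

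**Size, by simulation.** Same assumptions, Cox model with Efron ties, 36-month cut-off. Compare within a row or batch; the no-never-dosed HR is 0.727 in the 150-trial batch and 0.711 in the 40-trial batch.

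| Never dosed (olaparib + placebo) | Trials | Censored at DCO | Event at Day 1 | Censored at Day 1 |
|---|---|---|---|---|
| 0 + 1 | 150 | 0.770 | 0.722 | 0.727 |
| 1 + 0 | 150 | 0.715 | 0.731 | 0.728 |
| 3 + 1 | 150 | 0.731 | 0.733 | 0.728 |
| 0 + 4 | 40 | 0.856 | 0.691 | – |
| 4 + 0 | 40 | 0.671 | 0.724 | – |
| 8 + 4 | 40 | 0.755 | 0.717 | – |
| 26 + 13 | 40 | 0.806 | 0.737 | – |

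A second set of assumptions (260 and 131 patients, medians 25 and 14 months, all others off drug by week 108) agrees. One placebo patient moves the HR from 0.69 to 0.73. Two olaparib plus one placebo give 0.71, against 0.70 as Day 1 events.

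**Length of censoring.** In that second set, one never-dosed placebo patient gives 0.735 whether censored at 36 or at 84 months. The partial likelihood uses risk sets only at event times, so time after the last stop adds nothing.

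**The case against.** The strongest reply is that the harm is conditional. Never-dosed patients are a named deviation category, classified before database lock, so the sponsor knows who they are and may record a discontinuation date for them. The documents do not settle this. The objection stands as a limit on what can be claimed; it does not supply the missing rule.

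Lost patients may mostly be handled in practice. Protocol 5.9 describes withdrawal from study as covering investigational product and lists loss to follow-up as a reason. Drug is assigned at each dispensing visit, tablets are counted, and SAP 3.4.2 already uses a last dose date. This narrows the second group, but nothing ties those records to the TDT date. They also show that a last date on drug is available.

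The direction is not fixed. Never-dosed olaparib patients move the HR away from 1, and at 2:1 allocation a handful of patients largely cancels. That stands for small numbers; with 8 + 4 the gap is still about 0.04.

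Four stronger readings are tempting but unsupported:

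- **Everyone without a discontinuation record counts as on treatment for years.** Deaths are events, and the rest depends on the eCRF and on later vital status.
- **The distortion grows with each OS analysis.** It does not if nearly all others are off drug by about two years, as the 36 v 84 month comparison shows.
- **A never-dosed patient's later chemotherapy is not a TFST event**, because SAP 3.2.4 counts the "first subsequent therapy start date following study treatment discontinuation, or death". This is strained: the censoring sentence there asks only whether she had a further intervention of that type.
- **A new rule has no cost.** SAP section 5 shows that the PFS analysis, at which TDT was first due, has already taken place.

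**Conclusion.** The point holds as a defect in a stated rule. TDT is censored on vital status in a population that includes patients who never started drug, and no provision covers them. For a living never-dosed patient with no discontinuation record, the rule gives a wrong time on treatment.

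Under assumed inputs, the effect is about 0.04 to 0.05 on the HR, toward 1, for one placebo patient, and about 0.01 to 0.02 for one olaparib patient or for three split 2:1. Larger numbers, or an imbalance toward placebo, would matter more. These sizes rest on assumed stopping times, on almost everyone being off drug by about two years, and on never-dosed patients staying alive without a discontinuation date. Treatment continued past two years would soften them. The actual number of such patients is not in the documents.

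TDT is supportive and lies outside the PFS, PFS2 and OS testing procedure, so no primary or alpha-controlled conclusion is affected.

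**What to change.** - **SAP 3.2.6:** state that a never-dosed FAS patient has TDT set at Day 1 as an event, with censoring at Day 1 as a sensitivity analysis. The two gave nearly the same HR above (0.722 and 0.727 for one placebo patient).
- **SAP 3.2.6:** censor any other living patient without a discontinuation record at the last date known to be on study drug. For a patient confirmed on drug at the cut-off, that is still the cut-off date.
- **Protocol 11.1.2.6:** align the wording.
- **SAP 3.2.4 and 3.2.5:** as a clarification only, say that subsequent therapy in a never-dosed patient counts from randomisation.

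The cost is a few lines of text and a small derivation change. Because TDT was already due at the primary PFS analysis, the result under the current rule should be shown alongside for comparability, with the number of patients whose TDT changes in each arm.

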3.2.7 Time to earliest progression by RECIST or CA-125 or death

Progression or recurrence based on serum CA-125 levels will be defined on the basis of a progressive serial elevation of serum CA-125, according to the following modified Gynecologic Cancer Intergroup (GCIG) criteria (note GCIG criteria is not validated for this trial population):

• For patients with elevated CA-125 on or before the date of randomisation (i.e. greater than the upper limit of normal (ULN)):

- (a) If CA-125 does not fall to within the normal range post-randomisation then there must be evidence of CA-125 greater than, or equal to, 2 times the nadir value in the 28 day period before day 1 on 2 occasions at least 1 week apart
- (b) Where CA-125 does fall to within the normal range post-randomisation then there must be evidence of CA-125 greater than, or equal to, 2 times the ULN on 2 occasions at least 1 week apart
- Patients with CA-125 in the normal range on or before the date of randomisation and no results greater than ULN on or before the date of randomisation must show evidence of CA- 125 greater than, or equal to, 2 times the ULN on 2 occasions post-randomisation at least 1 week apart.
- CA-125 progression will be assigned the date of the first measurement that meets the above criteria.

Time to progression by RECIST or CA-125 progression or death is defined as the time from randomisation to the earlier date of RECIST or CA-125 progression or death by any cause.

Patients without a CA-125 progression or a RECIST progression who are still alive at the time of analysis will be censored at the time of their last evaluable RECIST assessment or their last available CA-125 measurement, whichever is the earliest at the time of the analysis. Since CA-125 is assessed more frequently than RECIST the two missed visit rule is based upon the RECIST schedule. Therefore if a patient dies, has RECIST progression or has CA-125 progression after two or more missed RECIST assessments, then the patient will be censored using at the last evaluable RECIST assessment where CA-125 was also collected. This will be defined as a RECIST assessment where the date of CA-125 sample is +/- 11 days (note the earliest date of the RECIST/CA-125 assessment will be used).

If only one assessment is missing during this period, no censoring is required. Patients that do not have any evaluable RECIST assessments or any CA-125 results post-randomisation will be censored at the date of randomisation.

Similarly to the primary analysis of PFS, RECIST progression will be determined from the investigator assessment of RECIST data.

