11.1.2.2 Time to earliest progression by RECIST 1.1 or CA-125 or death

Progression or recurrence based on serum CA-125 levels will be defined on the basis of a progressive serial elevation of serum CA-125, according to the following modified GCIG criteria (note GCIG criteria is not validated for this trial population):

- Patients with elevated CA-125 pre-treatment (i.e. greater than the upper limit of normal (ULN)):-
 - (a) If CA-125 does not fall to within the normal range whilst on treatment then there must be evidence of CA-125 greater than, or equal to, 2 times the nadir value in the 28 day period before day 1 on 2 occasions at least 1 week apart.
 - (b) Where CA-125 does fall to within the normal range whilst on study treatment (and the patient has not already progressed by way of (a) above) then there must be evidence of CA-125 greater than, or equal to, 2 times the ULN on 2 occasions at least 1 week apart.

- Patients with CA-125 in the normal range pre-treatment must show evidence of CA-125 greater than, or equal to, 2 times the ULN on 2 occasions at least 1 week apart. CA-125 progression will be assigned the date of the first measurement that meets the criteria as noted.

Time to progression by RECIST or CA-125 progression or death is defined as the time from randomisation to the earlier date of RECIST or CA-125 progression or death by any cause. Patients without a CA-125 progression or a RECIST progression who are still alive at the time of analysis will be censored at their last evaluable RECIST assessment or their last available CA-125 measurement, whichever is the most recent at the time of the analysis. If a patient progresses or dies after two or more missed RECIST and CA-125 assessments, then the patient will be censored at the time of their last evaluable assessment. If only one assessment is missing during this period, no censoring is required.

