6 CHANGES OF ANALYSIS FROM PROTOCOL

All efficacy and HRQoL will be analysed using FAS.

Section 3.2.1 Progression free survival

Added clarification that according to the RECIST 1.1 guidelines an overall visit response of PD also requires an absolute increase of > 5 mm in the sum of the diameters of the target lesions.

Section 3.2.7 Time to earliest progression by RECIST or CA-125 or death Derivations will be relative to randomization (CSP states start of study treatment). Also, censoring will use the earliest of the last evaluable RECIST assessment or the last available CA-125 measurement (CSP states most recent).

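### SAP 3.2.7 omits the protocol's condition on CA-125 branch (b), so a later normalisation can erase or re-date an earlier CA-125 progression, and falling values may be scored as progression, in the supportive RECIST/CA-125 endpoint

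*SAP*

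**What the plan says.** The rule concerns one group: "For patients with elevated CA-125 on or before the date of randomisation". It has two branches.

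- **Branch (a)**, for patients who do not normalise, requires at least "2 times the nadir value in the 28 day period before day 1 on 2 occasions at least 1 week apart". Protocol 11.1.2.2 uses the same reference value.
- **Branch (b)** requires at least 2 × ULN on two occasions at least a week apart. The documents differ on who enters it.
  - Protocol 11.1.2.2: "Where CA-125 does fall to within the normal range whilst on study treatment", with the added condition "and the patient has not already progressed by way of (a) above".
  - SAP 3.2.7: "Where CA-125 does fall to within the normal range post-randomisation then there must be evidence of CA-125". There is no such condition and no end to the window.

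The date rule in the SAP is: "CA-125 progression will be assigned the date of the first measurement that meets the above criteria".

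SAP Section 6 declares two changes for this endpoint. One is the time origin: "Derivations will be relative to randomization (CSP states start of study treatment". The other is the choice of censoring date. It does not mention the omitted condition.

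SAP 4.2.7 calls the endpoint supportive to PFS, with no multiplicity adjustment. RECIST progression and death are also events in it.

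**The concern.** Under the protocol, a patient who meets (a) has progressed, and nothing later undoes it. Under the SAP wording, her branch depends on whether CA-125 ever becomes normal after randomisation. A value months later, possibly produced by the next line of chemotherapy, can therefore change whether or when she progressed earlier. SAP 3.2.7 does not stop using CA-125 at subsequent therapy, although SAP 3.2.8 does so for best overall response.

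The wording also leaves open which values count under (b). Two programmers could follow SAP 3.2.7 faithfully, obtain different events for the same patient, and both differ from the protocol. At stake are the event dates, the log-rank result and the tabulated CA-125 progression counts for an endpoint named in the secondary objectives.

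**Working it through.** The documents give no event count, rate or power for this endpoint, so there is no stated figure to reproduce. The check applies each rule to constructed CA-125 series in multiples of ULN, so no ULN value has to be assumed.

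**Rules applied**

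- Threshold under (a) = 2 × nadir of the 28 days before day 1.
- Threshold under (b) = 2 × ULN, which is 2.0 in these units.
- Both need two values at least a week apart. The event takes the date of the first.
- Protocol: (a) until the first normal value. Then (b) on later values, only if (a) was not met.
- SAP reading 1: if any post-randomisation value is normal, (b) applies to values after normalisation only.
- SAP reading 2: if any post-randomisation value is normal, (b) applies to the whole post-randomisation series.

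**Series (week: value)**

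- **A.** Nadir 1.5, so the (a) threshold is 2 × 1.5 = 3.0. Values 4: 1.6, 8: 2.1, 12: 3.2, 16: 3.5, 24: 1.4, 28: 0.8, 36: 0.7.
- **B.** Nadir 3, so the (a) threshold is 2 × 3 = 6. Values 4: 2.6, 8: 2.2, 12: 1.2, 16: 0.8, 20: 0.7.
- **C.** An earlier value above ULN but 28-day nadir 0.8, so the (a) threshold is 2 × 0.8 = 1.6. Values 4: 1.2, 8: 1.7, 12: 1.8, 20: 0.9.

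| Case | Protocol | SAP reading 1 | SAP reading 2 |
|---|---|---|---|
| A | week 12 | none | week 8 |
| B | none | none | week 4 |
| C | week 8 | none | none |

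**Case A.** The values 3.2 and 3.5 exceed 3.0, so the protocol gives week 12. If the week-28 normal value came after study treatment ended, the protocol's on-treatment limit would also keep her in (a). Under the SAP she moves to (b). After week 28 nothing reaches 2.0, so reading 1 erases the event. Reading 2 counts 2.1 at week 8 and 3.2 at week 12, so the event moves to week 8. With the same rise but no later normal value, all three give week 12. The difference comes only from the later value.

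**Case B.** CA-125 falls steadily to normal, yet reading 2 scores 2.6 and 2.2 on the way down as progression at week 4. The protocol's (b) does not say in terms that its values must follow normalisation either. The table applies it that way, so this ambiguity is partly inherited.

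**Case C.** The values 1.7 and 1.8 exceed 1.6 but never reach 2.0, so both SAP readings lose the event. The pattern can occur. Protocol 4.1, criterion 6, requires a second sample when the first is above ULN, and that second value may be normal. SAP 3.2.7 reserves its normal-at-entry group for patients with no value above ULN up to randomisation, so this patient falls under (a)/(b). The protocol result assumes that she also counts as elevated pre-treatment there.

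**General relation.** If the nadir n exceeds ULN, then 2n > 2 × ULN, so any values that meet (a) also meet (b) when the whole series counts. With n above ULN, reading 2 can therefore move an event earlier or create one, but cannot remove one. Erasure needs reading 1, or n at or below ULN.

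**The case against.** **Erasure is not in the text.** SAP branch (b) nowhere says that the two values must follow normalisation. On the whole-series reading, a patient with nadir above ULN keeps her event. This stands, and a reader who infers that the SAP rule simply misses events goes further than the documents allow. It does not rescue the wording, because that same reading re-dates Case A and scores Case B as progression, and Case C is lost either way.

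**The clinical path limits the damage.** The protocol keeps patients on study treatment to RECIST progression even if CA-125 rises. Chemotherapy would then usually follow a RECIST event that already counts here. With scans every 12 weeks to week 156, the usual effect would be a later date and not a lost event. CA-125 testing after serological progression is also left to the investigator (Protocol 6.4.6.4), so the later normal value is not a scheduled measurement. Both points stand and reduce the likely size.

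**Section 6 covers the window.** The declared change of origin arguably explains why the SAP counts from randomisation. It says nothing about removing the end-of-treatment limit, and it does not cover the omitted condition.

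**The endpoint is supportive and its main analysis is past.** SAP 4.2.7 schedules it with the primary PFS analysis, and SAP Section 5 refers to that analysis as done. This stands. The action is partly to document what was done.

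**Conclusion.** The concern holds as an undeclared and ambiguous departure from the protocol. For patients with CA-125 above ULN by randomisation, SAP 3.2.7 lets later data decide an earlier event. As written, it can erase a CA-125 progression, re-date it (week 12 to week 8 in Case A), or count falling values as progression.

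The size in the trial cannot be computed. The number of patients with raised entry CA-125 is not given, nor how many later normalised. The cases are illustrations, not estimates. RECIST progression or death may still supply an event, and PFS, PFS2 and OS are unaffected. It is not known which rule was programmed, or whether the SAP version in force at the primary analysis had the same wording.

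A reader might also infer that branch (a) is wrong to use the pre-day-1 nadir in place of the lowest on-study value, and that this delays events more on olaparib. The documents do not support that as a defect. The reference is the same in both, both call the criteria modified and not validated in this population, and no difference between arms is shown. The choice can matter for an individual: with pre-day-1 nadir 5 × ULN, an on-study low of 1.3, values of 2.8 and 3.5 at weeks 12 and 16, and 10.5 and 12 at weeks 28 and 32, the event is at week 28 under both documents and week 12 with an on-study nadir. That is a design choice, at most worth an optional sensitivity analysis.

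**What to change.** In SAP 3.2.7:

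1. Restore the protocol's condition that (b) applies only to a patient who has not already progressed under (a).
2. Apply (a) and (b) in time order, using only values up to each sample date.
3. State that (b) counts only values after the first normalisation. Restoring the condition alone would not settle Case B.
4. State how CA-125 values after subsequent therapy are handled.
5. List any remaining departure from the protocol in Section 6.
6. State which rule was programmed for the reported analysis, and rerun this endpoint and its CA-125 progression table if it differs from the protocol.

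Leave the pre-day-1 nadir in branch (a) unchanged.

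The cost is a few lines of SAP text, a check of existing code, and at most a rerun of one supportive analysis on data already collected. Some CA-125 event dates may change from those already reported, and that should be disclosed.
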